20.4. PHYSICAL EXAMINATION

Weight and height are collected on eCRF.

Weight, height, and BMI will be summarized in demographics.

20.5. PREGNANCY TESTING

Pregnancy testing data (serum) will be collected for all woman of childbearing potential according to SoA. All pregnancy testing data will be listed.

Document: CCI

Author: PPD

Version Number:

3.0

Version Date:

19May2023

CCI

20.6. OTHER SAFETY ASSESSMENTS

20.6.1. CLINICAL TRIAL REGISTRY ANALYSES

Additional analyses will be performed for the purpose of fulfilling the Clinical Trial Registry (CTR) requirements. These analyses will be the responsibility of the Sponsor.

Analyses provided for the CTR requirements include the following:

A summary of AEs will be provided as a dataset which will be converted to an XML file. Both SAEs and "Other" AEs are summarized: by treatment group, by MedDRA Preferred Term.

21. GENETIC ANALYSIS

Not applicable.

Document: CCI

Author: PPD

Version Number:

3.0

Version Date:

19May2023

CCI

APPENDIX 1. PROGRAMMING CONVENTIONS FOR OUTPUTS

Output Conventions

Outputs will be presented as shown in the Output shells.

If the original data has N decimal places, then the summary statistics should have the following decimal places:

- Minimum and maximum: N
- Mean (and LS Means), median: N + 1
- SD or SE: N + 2

Percentages will be reported to one decimal place. Where counts are zero, percentages will not appear in the output.

P-values will be reported to three decimal places, except values <1.000 but >0.999 will be presented as “>0.999” (eg, 0.9998 is presented as >0.999). P-values <0.001 will be presented as “<0.001” (eg, 0.0009 is presented as <0.001). Rounding will be applied after the <0.001 and >0.999 rule.

Dates & Times

Depending on data available, dates and times will take the form yyyy-mm-ddThh:mm:^{PPD}

Spelling Format

English US.

Presentation of Treatment Groups

For outputs, treatment groups will be represented as follows and in the given order:

Treatment Group	For Tables and Graphs	For Listings (include if different to tables)
Galcanezumab 120 mg SC once monthly	Galcanezumab	Galcanezumab
Rimegepant 75 mg ODT every other day	Rimegepant	Rimegepant
Not Randomized		Not Randomized

Presentation of Visits

For outputs, visits will be represented as follows and in that order:

Document: **CCI**

Author: **PPD**

Version Number:

3.0

Version Date:

19May2023

CCI

Long Name (default)	Short Name
Screening (Visit 1)	Scr (V1)
Baseline (Visit 2)	BL (V2)
Randomization (Visit 3)	RND (V3)
Month 1 (Visit 4)	M1 (V4)
Month 2 (Visit 5)	M2 (V5)
Month 3 (Visit 6)	M3 (V6)

Listings

All listings will be ordered by the following (unless otherwise indicated in the template):
 Randomized treatment group (or treatment received if it's a safety output), first by Galcanezumab and then Rimegepant,
 Center-subject ID,
 Date (where applicable),
 For listings where non-randomized participants are included, these will appear in a category after the randomized treatment groups labeled "Not Randomized".

Document: CCI

Author: PPD

Version Number: 3.0

Version Date: 19May2023

APPENDIX 2. PARTIAL DATE CONVENTIONS

Imputed dates will NOT be presented in the listings.

ALGORITHM FOR TREATMENT EMERGENCE OF ADVERSE EVENTS:

AE START DATE	AE STOP DATE	ACTION
Known	Known/Partial/ Missing	If start date < study med start date, then not TEAE If start date >= study med start date, then TEAE
Partial, but known components show that it cannot be on or after study med start date	Known/Partial/ Missing	Not TEAE
Partial, could be on or after study med start date OR Missing	Known	If stop date < study med start date, then not TEAE If stop date >= study med start date, then TEAE
	Partial	Impute stop date as latest possible date (i.e. last day of month if day unknown or 31st December if day and month are unknown), then: If stop date < study med start date, then not TEAE If stop date >= study med start date, then TEAE
	Missing	Assumed TEAE

Document: **CCI**

Author: **PPD**

Version Number:

3.0

Version Date:

19May2023

CCI

AE START DATE	AE STOP DATE	ACTION

ALGORITHM FOR PRIOR / CONCOMITANT MEDICATIONS:

CM START DATE	CM STOP DATE	ACTION
Known	Known	If stop date < study med start date, assign as prior If stop date >= study med start date and start date <= end of double-blind treatment period, assign as concomitant
	Partial	Impute stop date as latest possible date (i.e. last day of month if day unknown or 31st December if day and month are unknown), then: If stop date < study med start date, assign as prior If stop date >= study med start date and start date <= end of double-blind treatment period, assign as concomitant
	Missing	If stop date is missing could never be assumed a prior medication If start date <= end of double-blind treatment period, assign as concomitant
Partial	Known	Impute start date as earliest possible date (i.e. first day of month if day unknown or 1st January if day and month are unknown), then: If stop date < study med start date, assign as prior If stop date >= study med start date and start date <= end of double-blind treatment period, assign as concomitant

Document: **CCI**Author: **PPD**

Version Number:

3.0

Version Date:

19May2023

CM START DATE	CM STOP DATE	ACTION
	Partial	
Impute start date as earliest possible date (i.e. first day of month if day unknown or 1st January if day and month are unknown) and impute stop date as latest possible date (i.e. last day of month if day unknown or 31st December if day and month are unknown), then:
 
If stop date < study med start date, assign as prior
 
If stop date \geq study med start date and start date \leq end of double-blind treatment period, assign as concomitant

	Missing	
Impute start date as earliest possible date (i.e. first day of month if day unknown or 1st January if day and month are unknown), then:
 
If stop date is missing could never be assumed a prior medication
 
If start date \leq end of double-blind treatment period, assign as concomitant

Missing	Known	
If stop date < study med start date, assign as prior
 
If stop date \geq study med start date, assign as concomitant

	Partial	
Impute stop date as latest possible date (i.e. last day of month if day unknown or 31st December if day and month are unknown), then:
 
If stop date < study med start date, assign as prior
 
If stop date \geq study med start date, assign as concomitant

	Missing	Assign as concomitant

Document: CCI

Author: PPD

Version Number: 3.0

Version Date: 19May2023

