##### **9.3.4.1. Treatment-Emergent Adverse Events**

TEAEs are defined as the reported AEs that first occurred or worsened during the postbaseline period compared with the baseline period. For each TEAE, the reported severity level of the event (mild, moderate, or severe) will be determined by physician opinion. The MedDRA LLT will be used in the treatment-emergent computation. For each LLT, the maximum severity at baseline will be used as the baseline severity. If the maximum severity during postbaseline is greater than the maximum baseline severity, the event is considered to be treatment-emergent for the specific postbaseline period. Safety analyses for each study period will use all visits up through the last scheduled visit in the prior study period as baseline. For each participant and TEAE, the maximum severity for the MedDRA level being displayed (preferred term, High-Level Term, or System Organ Class [SOC]) is the maximum postbaseline severity observed from all associated LLTs mapping to that MedDRA level.

For events that are sex-specific, the denominator and computation of the percentage will include only participants from the specific sex.

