20.1. ADVERSE EVENTS

Adverse Events (AEs) will be coded using MedDRA central coding dictionary, Version 24.1 or higher. Treatment-emergent adverse events are defined as the reported AEs that first occurred or worsened during the post-baseline phase compared with baseline phase. Adverse events (AE) that occurred on the visit date of Visit 3 will be determined to be pre-dose or after dose based on AE start time and the injection time: pre-dose if AE start time is before the injection time; post dose if AE start time is after the injection time.

For each TEAE, the severity level of the event (mild, moderate, or severe) will be determined by participant or physician opinion. The MedDRA Lowest Level Term (LLT) will be used in the treatment emergent computation. For each LLT, the maximum severity at baseline will be used

Document: CCI

Author: PPD

Version Number:

3.0

Version Date:

19May2023

CCI

as the baseline severity. If the maximum severity during post-baseline is greater than the maximum baseline severity, the event is considered to be treatment emergent for post-baseline period. For each participant and TEAE, the maximum severity for the MedDRA level being displayed (PT) is the maximum post-baseline severity observed from all associated LLTs mapping to that MedDRA level. Summary tables will present events by PT by decreasing frequency of PT or by SOC/PT and by decreasing frequency of PT within SOC.

See APPENDIX 2 for handling of partial dates for AEs. In the case where it is not possible to define an AE as treatment emergent or not, the AE will be classified by the worst case; i.e. treatment emergent.

An overall summary of number of participants within each of the categories described in the sub-section below, will be provided as specified in the templates. Listings will include TEAEs and Non-TEAEs.

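### SAP Appendix 2 settles treatment emergence from dates alone, SAP 20.1 and Protocol 9.3.4.1 require a severity comparison, and no text says which rule prevails

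*SAP*

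**What the plan says.** Protocol 9.3.4.1 gives the definition: "TEAEs are defined as the reported AEs that first occurred or worsened during the postbaseline period compared with the baseline period". It applies this by LLT: "If the maximum severity during postbaseline is greater than the maximum baseline severity, the event is considered to be treatment-emergent". SAP 20.1 repeats both parts. TEAEs are events that "first occurred or worsened during the post-baseline phase compared with baseline phase", and the test is again by LLT: "If the maximum severity during post-baseline is greater than the maximum baseline severity". Table F in SAP 6.2 fits this rule. For TEAEs it takes all of Visits 1 to 3 as baseline and everything after Visit 3 up to Visit 6 as post-baseline.

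SAP 20.1 sends the reader to Appendix 2 for partial AE dates. It adds a worst-case default: an event that cannot be classified counts as treatment-emergent.

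Appendix 2 is titled as a set of partial-date conventions, but its AE table is headed as the algorithm for treatment emergence. The table has three groups of rows:

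- **Start date known.** "If start date < study med start date, then not TEAE"; "If start date >= study med start date, then TEAE".
- **Start date partial but certainly before dosing.** Not a TEAE, whatever the stop date.
- "Partial, could be on or after study med start date OR Missing". The stop date decides, completed to its latest possible value if partial. If it is missing, the event is assumed to be a TEAE.

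Severity, worsening and LLT appear in none of these rows.

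**The concern.** A table that carries the name of the algorithm and ends in a yes/no verdict is what a programmer would code. If it is coded as it stands, the TEAE flag no longer means first occurrence or worsening relative to baseline. It means that the record began, or in some rows ended, on or after first dose.

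That flag feeds most of the safety output in SAP 20.1: incidence by preferred term and by system organ class, maximum severity, relationship, serious TEAEs, the category of other (non-serious) AEs, TEAEs leading to discontinuation of study intervention, and injection-site TEAEs. It also feeds the registry summary in SAP 20.6.1. SAP 20 and Protocol 9.3.4 compare the arms on categorical safety measures with Fisher's exact test. Two programmers who follow different sections of the same SAP could produce different TEAE tables.

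**Working it through.** The plan states no figure to reproduce here, so the check is to apply both rules to the same records. Code severity as 0 = none, 1 = mild, 2 = moderate, 3 = severe. Let b be the maximum baseline severity and p the maximum post-baseline severity for one LLT.

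- Severity rule (SAP 20.1, Protocol 9.3.4.1): TEAE if p > b.
- Appendix 2, known start date: TEAE if the start date is on or after the first dose of study medication.

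**Case A: one record, pre-dose start, event continuing after dosing.** b and p each run from 1 to 3, giving 3 × 3 = 9 combinations. Appendix 2 says not TEAE in all 9.

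| b → p | Severity rule | Appendix 2 |
|---|---|---|
| 1→2, 1→3, 2→3 | TEAE | not TEAE |
| the other 6 (unchanged or milder) | not TEAE | not TEAE |

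The rules disagree in 3 of 9, and all three are worsenings. This case requires a record that keeps its pre-dose start date and also shows a later, higher severity.

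**Case B: a record that starts on or after dosing.** b runs from 0 to 3 and p from 1 to 3, giving 4 × 3 = 12 combinations. Appendix 2 says TEAE in all 12.

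| b → p | Severity rule | Appendix 2 |
|---|---|---|
| 0→1, 0→2, 0→3 (absent at baseline) | TEAE | TEAE |
| 1→2, 1→3, 2→3 (new record, more severe) | TEAE | TEAE |
| 1→1, 2→2, 3→3 (unchanged recurrence) | not TEAE | TEAE |
| 2→1, 3→1, 3→2 (milder recurrence) | not TEAE | TEAE |

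The rules disagree in 6 of 12, and all six are recurrences at the same or lower severity. This case needs only a baseline record and a later record of the same term.

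These are counts of logical cases, not expected frequencies.

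**Partial and missing dates.** These are the dates that 20.1 does send to Appendix 2. A partial start that can only be pre-dose is rejected without looking at severity. A missing start with a stop on or after first dose is accepted without looking at severity, even where the same LLT was recorded at baseline at equal or higher severity. Start date is therefore not the criterion in every row, but no row uses severity.

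**Which rule is intended.** Three places point to the severity rule:

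- Table F's baseline of Visits 1 to 3 would serve no purpose for TEAEs under a date-only rule.
- The severity paragraph of SAP 20.1.1 singles out TEAEs that start after first dose, a qualifier that adds little if every TEAE starts on treatment.
- SAP 3.3 lists only added exploratory objectives and endpoints as changes from the protocol, so a date-only definition would be an undeclared change.

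**Room for pre-dose records.** AEs are collected from consent (Protocol 8.3.1). Screening lasts 3 to 30 days and baseline 30 to 40 days, with up to 5 more to schedule Visit 3. The window is 3 + 30 = 33 to 30 + 40 + 5 = 75 days. Pre-dose records of a term can therefore occur, but the documents give no AE rates from which to say how often.

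**The case against.** The strongest reply is that the documents already show which rule governs. The appendix title concerns partial dates, SAP 20.1 cites it only for those, and the severity rule is written out in full in both documents. On that reading the appendix only places records before or after first dose, and 20.1 then compares severity. This is probably what was meant. It does not account for a known-date row that ends in a verdict, and no sentence says that 20.1 prevails.

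A second reply concerns worsening. A reader might infer from Appendix 2 that events which worsen on treatment will be dropped. The documents do not support that as a fact, because they do not describe the AE record layout. If a worsening is entered as a new record with a post-dose start, Appendix 2 counts it, in agreement with 20.1. If one record holds one severity, 20.1 would not see the worsening either. Only a layout with a pre-dose start and a later, higher severity in the same record gives the conflict. Protocol 10.3.1 makes exacerbation of a pre-existing condition an AE but does not say how it is recorded. This reply stands, so that direction is conditional.

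A third reply is that little would disappear from view. Listings include TEAEs and non-TEAEs, all SAEs are summarized, and AEs leading to study discontinuation are summarized without a TEAE restriction. This stands too, but it does not correct the TEAE tables.

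**Conclusion.** The conflict is real. For known start dates, Appendix 2 states a rule that contradicts SAP 20.1 and Protocol 9.3.4.1. For the partial and missing dates referred to it, it also decides without severity. The over-count of unchanged or milder recurrences follows from the text alone. The exclusion of worsening holds only if a worsened event keeps its pre-dose start date and the higher severity is captured in that record.

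The size cannot be derived from the documents. A reader might infer from the long pre-dose window that recurrences will be common, or assume a prevalence and a recurrence fraction and compute a number of participants. Neither document gives AE rates to support that. Nor do they support a claim that one arm would be favoured: pre-dose records arise before randomization, and nothing is given on recurrence by arm. What is affected is the TEAE counts and percentages and their Fisher's exact comparisons. The primary, key secondary and other efficacy analyses are untouched.

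**What to change.** In Appendix 2, replace the two verdicts in every row by post-baseline record and baseline record, and retitle the table as assignment of AE records to period. For events on the Visit 3 date, carry over the comparison of AE start time with injection time that 20.1 already sets. Then add three statements:

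1. Once records are assigned, treatment emergence is decided only by the LLT severity comparison in SAP 20.1.
2. How an increase in severity of an event with a pre-dose start is assigned to the post-baseline period, given how the CRF records it: by a new record, or by a dated severity change within the record. If the CRF holds one severity per record and no new record is required, say that such worsening cannot be identified.
3. The worst-case rule remains for dates that cannot be resolved.

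The cost is SAP wording and one programming specification. The period assignment and the recurrence rule need no new data. Whether worsening can be detected depends on what the CRF already captures, which should be checked before the second statement is written.

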APPENDIX 3. DESCRIPTION OF IMPORTANT PROTOCOL DEVIATIONS

Category	Subcategory	Study-specific	Source	Comments
ICF	ICF not obtained	Initial ICF date is missing or is after (Visit 1 date or Visit 1 lab date)	Programmable - Stats	
	Improper ICF	ICF not signed prior to initiation of protocol procedures	Non-programmable - Monitor identified	
	Improper ICF	Patient not provided ICF in language appropriate for this study and their language proficiency (English or US Spanish)	Non-programmable - Monitor identified	
Eligibility	Inclusion/ Exclusion	Age <18 or >65 years old at study entry (if enrolled under Amendment A)	Non-programmable- Monitor identified	
		Age <18 or >75 years old at study entry (if enrolled under Amendment B or later)	Non-programmable- Monitor identified	
		Number of migraine headache days <4 or >14 per 30-day period at baseline	Programmable - Stats	Based on normalized number of migraine headache days.
		Number of migraine attack <2 per 30-day period at baseline	Programmable - Stats	Based on normalized number of migraine headache days.
		Baseline ePRO compliance <80%	Programmable - Stats	
		Female patients have a positive serum pregnancy test prior to randomization visit	Programmable - Stats	

Document: CCI

Author: PPD

Version Number: 3.0

Version Date: 19May2023

Category	Subcategory	Study-specific	Source	Comments
Eligibility	Inclusion/ Exclusion	Patient is pregnant at time of randomization	Non-programmable-Monitor identified	
		Insufficient washout of prohibited migraine preventive medication for at least 5 days prior to Visit 2	Programmable - Stats	Patients must have discontinued such treatment at least 5 days prior to Visit 2.
		Insufficient Washout of Botulinum toxin A and B at least 3 months prior to Visit 2 if for therapeutic use	Non-Programmable-Study Team identified	1) Stats will create the list of patients who meet this IPD criteria. 2) Among those, the true IPDs will be manually added into non-programmable Excel spreadsheet. 3) A month may be defined as 4 weeks.
		Insufficient Washout of Nerve Block or Device Use in the head or neck area or for migraine prevention at least 30 days prior to Visit 2	Non-Programmable-Study Team identified	1) Stats will create the list of patients who meet this IPD criteria. 2) Among those, the true IPDs will be manually added into non-programmable Excel spreadsheet.
		Current or prior exposure to a CGRP antagonist	Non-Programmable-Study Team identified	1) Stats will create the list of patients who meet this IPD criteria. 2) Among those, the true IPDs will be manually added into non-programmable Excel spreadsheet.
		BMI ≥ 40 at baseline	Programmable - Stats	
		Positive or No urine drug screen prior to randomization	Programmable - Stats	For randomized patients if prior to Visit 3, a patient has a positive UDS result and a repeated UDS not done or last repeat UDS is positive or UDS never collected.
		Other inadvertent enrollment which is deemed clinically important by Lilly Medical	Non-Programmable-Study Team identified	Not all inadvertent enrollments will necessarily be considered clinically important.

Document: CCI

Author: PPD

Version Number: 3.0

Version Date: 19May2023

Category	Subcategory	Study-specific	Source	Comments
Data Quality	Missing Data	Diary compliance <=50% for half or more of patient's double-blind treatment phase participation	Programmable – Stats	
With <=50% ePRO compliance rate for half or more months of double-blind treatment phase, where "month" refers to a dosing interval. For example,
 
 • if patient remained in the study for 3 months (i.e., dose intervals), and >=2 months have epro compliance <=50%. • if patient remained in the study for 1 or 2 months (i.e., dose intervals), and >=1 months have epro compliance <=50%. 
Lost to follow-up patients' last month interval should not be included in the consideration above.
 
If a patient discontinued before Visit 4 or if total time in double-blind period was less than 2 weeks, the patient should not be counted here.

		Missing safety measurement: vital signs (Blood pressure, body temperature, pulse) at baseline or in SP III		
For randomized patients, if blood pressure, body temperature, or pulse are missing all baseline measures or missing all post-baseline measures during the double-blind treatment period.
 
For patients who discontinued due to "lost to follow up", if all postbaseline measures are missing, it is not an important protocol deviation

		Missing safety measurement: Chemistry or Hematology at baseline or in SP III	Programmable – Stats	
For randomized patients, if calcium and hemoglobin are missing all baseline measures, or if there is non-missing Visit 6 or early termination data and missing the post-baseline measures in the double-blind treatment period.
 
For patients who discontinued due to "lost to follow up", if all post-baseline measures are missing, it is not an important protocol deviation.

Document: CCI

Author: PPD

Version Number: 3.0

Version Date: 19May2023

Category	Subcategory	Study-specific	Source	Comments
Data Quality	Missing Date	Missing safety measurement: ECGs at baseline and in SP III	Non-programmable-Monitor identified	Same rule as for "Missing safety measurement: Chemistry or hematology at baseline or in SP III".
		Missing hepatic follow-up labs	Non-Programmable-Study Team identified	
	Treatment Assignment/ Randomization Error	IWRS data entry errors that impact patient stratification	Programmable – Stats	If migraine headache day categories (<8 vs ≥8) from IWRS was different from derived from ePRO.
Study Procedures	Discontinuation	Participant met at least one criterion for Study intervention discontinuation, but continued with dosing	Non-programmable-Monitor identified	
		Participant met at least one criterion for Study discontinuation, but continued in the study with dosing	Non-programmable-Monitor identified	
	Excluded Conmeds	Taking prohibited migraine preventive medication for primary study indication for >7 consecutive days during SP II or III	Programmable - Stats	Prior therapy should be excluded in the consideration.
		Taking prohibited migraine preventive medication for any indication for >7 consecutive days during SP II or III	Programmable - Stats	Prior therapy should be excluded in the consideration.

Document: CCI

Author: PPD

Version Number: 3.0

Version Date: 19May2023

Category	Subcategory	Study-specific	Source	Comments
Study Procedures	Excluded Conmeds	Taking Botulinum toxin A and B in the head or neck for therapeutic indication during SP II or III	Non-Programmable- Study Team identified	1) Stats will create the list of patients meet this IPD criteria. 2) Among those, the true IPDs will be manually added into non-programmable excel sheet.
		Opioid, barbiturate, or steroid use >7 consecutive days during SP II or III	Programmable - Stats	Prior therapy should be excluded in the consideration.
		Any use of NURTEC (rimegepant) during SPII or III as a concomitant medication	Non-Programmable- Study Team identified	1) Stats will create the list of patients meet this IPD criteria. 2) Among those, the true IPDs will be manually added into non-programmable excel sheet.
		Taking prohibited CGRP antagonist (oral; except rimegepant) for >7 consecutive days during SPII or III	Non-Programmable- Study Team identified	1) Stats will create the list of patients meet this IPD criteria. 2) Among those, the true IPDs will be manually added into non-programmable excel sheet.
		Any use of a CGRP antagonist (monoclonal antibody) during SPII or III as a concomitant medication	Non-Programmable- Study Team identified	1) Stats will create the list of patients meet this IPD criteria. 2) Among those, the true IPDs will be manually added into non-programmable excel sheet.
Investigational Product	Medication not fit for use	Patient received drug that was declared "Not Fit for Use"	Non-programmable - Monitor identified	
	Dosing Error	Significant violations of study drug dosing	Non-programmable - Monitor identified and Study Team identified	1) Stats will create the list of patients who have incorrect dosing (not including skipped dose). 2) Monitors will identify other events not able to be captured by programming (such as switched IP packages) 3) Medical will review both lists and identify IPDs to be manually added into non-programmable Excel sheet.
	Injection Schedule	Skipped dose of study drug	Programmable - Stats	Will not be a protocol deviation if the patient's study intervention was withheld by the investigator for safety reasons

Document: CCI

Author: PPD

Version Number: 3.0

Version Date: 19May2023

Category	Subcategory	Study-specific	Source	Comments
Investigational Product	ODT schedule	Taking <80% or >120% of prescribed ODT doses	Programmable - Stats	Will not be a protocol deviation if the patient's study intervention was withheld by the investigator for safety reasons
	Unblinding	Unjustified un-blinding of patient treatment assignment	Non-programmable - Monitor identified	
Administrative/ Oversight	Suspected misconduct	Suspected Fraud	Non-programmable - Monitor identified	
	Patient privacy violation	Privacy Breach	Non-programmable - Monitor identified	This will only include those events which result in a full de-identification of the patient.
Safety	Other	Site did not appropriately report SAE	Non-programmable - Monitor identified	Failure to report an SAE within a reasonable timeframe relative to the requirement of within 24 hours of the investigator being made aware of the SAE (for example 28 hours would not be an important deviation); Failure to respond to SAE queries.
		Dosed female has positive pregnancy test during the treatment phase and not discontinued from treatment	Non-programmable - Monitor identified	

Abbreviations: BMI = body mass index; Conmeds = concomitant medications; ICF = informed consent form; IPD=important protocol deviations; ePRO= electronic patient reported outcome; SAE = serious adverse event.

Document: CCI

Author: PPD

Version Number: 3.0

Version Date: 19May2023

CCI

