A 50% responder (Participant with $\geq 50\%$ reduction from baseline in migraine headache days): is defined as Yes, if any participant who has a $\geq 50\%$ reduction in the total number of migraine headache days in a 30-day period relative to baseline period, as No if otherwise. Therefore, if the percent change from baseline in the number of migraine headache days is $\geq 50\%$, the participant will be counted as an 50% responder.

Change from baseline in the number of monthly migraine headache days in each 30-day period will be summarized from daily data for each patient in that period (including approximately 30 days of daily data from the baseline period prior to randomization, 3 months of daily data during double-blind treatment period).

The daily ePRO data will reflect whether the patients meet the migraine / probable migraine criteria; those data will be aggregated, and the number of migraine headache days will be provided for each of the 30-day periods.

18.1.2. ADJUSTING FOR THE NUMBER OF DAYS WITH NON-MISSING DIARY DATA IN THE PERIOD:

In calculating the number of migraine headache days for each period, if the period is not equal to 30 days, the number of migraine headache days will be adjusted by multiplying the number of migraine headache days by $(30/x)$ where “x” is the total number of non-missing diary days in the period.

This approach to missing ePRO diary data assumes that the rate of migraine headaches per day is the same with missing and non-missing ePRO diary days, and it is missing at random. The same approach will also be applied to secondary and exploratory measures that are derived from the ePRO data.

Additionally, if the ePRO compliance rate (please refer to Section 17) for a monthly interval is $\leq 50\%$, then all endpoints to be derived from the ePRO diary data for that one-month period will be considered missing. For a participant who discontinued early in the double-blind treatment

Document: **CCI**

Author: **PPD**

Version Number:

3.0

Version Date:

19May2023

CCI

phase, compliance rate for the last month of that study period will be calculated with the denominator of the maximum of 30 and the total number of calendar days in that month.

Secondary and Exploratory Migraine and Headache Measures

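### Applied as written, the diary-compliance deviation rule flags a complete diary when a participant leaves in the first half of Month 2 for any reason other than loss to follow-up

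*SAP*

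**What the plan says.** The row is in SAP Appendix 3, under Data Quality, Missing Data. Its title is "Diary compliance <=50% for half or more of patient's double-blind treatment phase participation". The comment column restates this as "With <=50% ePRO compliance rate for half or more months of double-blind treatment phase", defines a month as a dosing interval, and gives two worked cases:

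- Three intervals: "if patient remained in the study for 3 months (i.e., dose intervals), and >=2 months have epro compliance <=50" percent.
- One or two intervals: "if patient remained in the study for 1 or 2 months (i.e., dose intervals), and >=1 months have epro compliance <=50" percent.

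Two exemptions follow. The first drops an interval: "Lost to follow-up patients' last month interval should not be included in the consideration above". The second removes the participant from the row altogether: "If a patient discontinued before Visit 4 or if total time in double-blind period was less than 2 weeks". The row is marked as programmable and, unlike several other rows, has no step in which the study team picks out the true deviations.

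The compliance rate is defined in SAP 17.1 as actual over expected diary days. Expected days run from the injection that opens the interval to the injection that closes it, plus 1. SAP 18.1.2 adds a rule for early discontinuers: the last month's rate is "calculated with the denominator of the maximum of 30 and the total number of calendar days in that month".

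SAP 9.2 says that important deviations are tabulated and listed for the ITT set by randomized arm and overall.

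**The concern.** The 30-day floor in 18.1.2 suits its purpose there, which is to set a month's endpoints to missing when too little of the month was observed. Appendix 3 asks something else: whether the participant kept the diary while taking part. If the same floor is carried over, a short stay in Month 2 looks like poor diary keeping.

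What is at stake is the accuracy of a reported by-arm table. Participants who leave soon after Visit 4 because of an adverse event, lack of efficacy or their own decision would be listed as important diary-quality deviations even if they missed no entry. Someone with the same entries who was lost to follow-up would not be listed.

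**Working it through.** **Inputs**

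- Flag rule, both exemptions and the definition of month: SAP Appendix 3, diary-compliance row.
- Last-month denominator for an early discontinuer, max(30, calendar days in that month): SAP 18.1.2.
- General compliance formula: SAP 17.1.
- A month is 30 days: SAP 6.4. Month 2 begins at Visit 4: SAP 15.

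**Step 1. Reproduce the plan's trigger counts.** Half or more of m intervals means at least ceil(m/2). For m = 1, 2, 3 this gives 1, 1, 2, which matches the two worked cases in Appendix 3.

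**Step 2. Find the denominator for a Month 2 leaver.** The 17.1 formula needs a closing injection. A participant who leaves in Month 2 has no Visit 5 injection, so 17.1 gives no value. Appendix 3 gives no formula of its own. The rule in 18.1.2 is the one stated rule for this participant, and it refers to the Section 17 compliance rate.

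**Step 3. Score a complete diary.** Take a participant who leaves on day k of an interval with an entry for every day.

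- A completed 30-day interval has 30 - 0 + 1 = 31 expected days under 17.1, so it scores 30/31 = 97% or 31/31 = 100%. It is far above 50% either way.
- The truncated interval scores k/max(30, k) = k/30 for k up to 30.
- k/30 <= 0.50 when k <= 15.

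| Leaves, not lost to follow-up | Last-interval rate | Intervals at <=50% | Needed | Flag |
|---|---|---|---|---|
| Month 1, any day | not assessed | not assessed | not assessed | exempt (before Visit 4) |
| Month 2, day 10 | 10/30 = 33.3% | 1 of 2 | 1 | yes |
| Month 2, day 15 | 15/30 = 50.0% | 1 of 2 | 1 | yes |
| Month 2, day 16 | 16/30 = 53.3% | 0 of 2 | 1 | no |
| Month 3, day 10 | 10/30 = 33.3% | 1 of 3 | 2 | no |

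The participant who leaves on day 10 of Month 2 has 30 + 10 = 40 of 40 entries and is flagged. The flagged leaving days in Month 2 are exactly 1 to 15. The diary asks about the previous day, so if the leaving day itself has no entry the rate is (k - 1)/30 and the window is days 1 to 16.

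**Step 4. Apply the exemptions.** For a lost-to-follow-up participant leaving in Month 2, the last interval is dropped. One interval remains, at about 100%, and there is no flag on any of the 30 days. The other exemption covers leaving before Visit 4 or spending less than 2 weeks in the double-blind period. A Month 2 leaver has passed Visit 4 and has been in the period for about 30 days or more, so it cannot apply.

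**Step 5. Apply either remedy.** If the truncated interval is dropped for every early discontinuer, or is scored as k/k = 100%, a complete diary is flagged on 0 of 30 Month 2 leaving days, against 15 of 30 under the current text.

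**The case against.** The best reply is that the 30-day denominator is imported. Appendix 3 does not cite 18.1.2, and that paragraph concerns when endpoints are set to missing. Section 17.1 also has no closing injection for Month 3 in completers, because the last injection is at Visit 5. Programmers must therefore already extend it to some other end date. Extending it to the exit date would give 10/10 rather than 10/30, and no flag. This stands in part: Appendix 3 leaves the denominator unstated. But for early discontinuers the SAP does state a rule, and it is the 30-day one. A programmer who follows the text arrives there.

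A second reply is that only completed intervals may count. Someone who leaves 10 days after Visit 4 would then have one interval, at about 100%. If every started interval counted, the one-month case would be nearly empty, since leavers before Visit 4 are exempt. This reading is weaker. Dropping the last interval for lost-to-follow-up participants is needed only if truncated intervals otherwise count, and dropping it for a Month 2 leaver itself produces the one-month case.

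A third reply is that the row sits under Missing Data and that 18.1.2 does set this participant's Month 2 endpoints to missing, so the flag marks a real loss. The loss is real, but a lost-to-follow-up participant with the same entries loses the same month and is not flagged. The row title also refers to compliance during participation, and early departure is reported under disposition in SAP 9.1.

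A reader might go further and infer that the primary result, or the quality of the data behind it, is misstated. The documents do not support that. SAP Section 5 defines only ITT and safety sets, there is no per-protocol set, and no efficacy analysis uses the flag. Diary compliance is also compared between arms separately in Section 17.

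**Conclusion.** The point holds as a small defect in a reported table. Under the stated rules, a complete diary is coded as an important missing-data deviation when the participant leaves on days 1 to 15 after Visit 4 for a reason other than loss to follow-up.

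This rests on two readings: that the 18.1.2 denominator governs this row, and that a truncated interval counts as a month. Both are the more natural readings, but Appendix 3 states neither outright. If the sponsor intends otherwise, the row still needs to say so.

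A reader might want a count of false flags, or infer an imbalance between arms. Neither can be derived. The protocol and SAP give a dropout rate of no more than 10% of about 575, which is a ceiling. They give no timing of withdrawal, no split by reason and no difference by arm. Protocol 7.1 also asks participants who stop treatment to stay in the study, which narrows the group. Severity is low, and the case for changing the text is that the correction is cheap.

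**What to change.** In the diary-compliance row of SAP Appendix 3, do one of the following:

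1. Leave out the truncated last interval for every participant who discontinues early, as the row already does for lost to follow-up.
2. Compute compliance for that interval, in this row only, over the days the participant was actually in the study.

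The options differ for Month 3 leavers with one poor completed month. Option 1 makes that 1 of 2 intervals, which is flagged. Option 2 keeps three intervals, so it is 1 of 3 and not flagged if the last diary was kept up. The sponsor should choose with that in view.

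Either way, state whether a truncated interval counts as a month, and leave the 30-day denominator in 18.1.2 unchanged for deriving endpoints. The cost is a sentence or two in Appendix 3 and a small programming change, with no effect on efficacy derivations.
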